**Ipilimumab dose discontinuation:**

- Any Grade 2 drug-related uveitis, eye pain or blurred vision that does not respond to topical therapy and does not improve to Grade 1 severity within the re-treatment period OR requires systemic treatment
- Any Grade 2-3 bronchospasm or other hypersensitivity reaction
- Any Grade 3 non-skin, drug-related adverse event with the following exceptions for laboratory abnormalities, grade 3 nausea and/or vomiting, grade 3 neutropenia or thrombocytopenia, and symptomatic endocrinopathies which resolved (with or without hormone substitution)
- Any drug-related liver function test (LFT) abnormality that meets the following criteria requires discontinuation:
  - AST or ALT > 8x ULN
  - Total bilirubin > 5x ULN
  - Concurrent AST or ALT > 3x ULN and total bilirubin > 2x ULN
- Any Grade 4 drug-related adverse event or laboratory abnormality, except for the following events which do not require discontinuation:
  - Grade 4 neutropenia ≤ 7 days
  - Grade 4 lymphopenia or leukopenia
  - Isolated Grade 4 amylase or lipase abnormalities that is not associated with symptoms or clinical manifestations of pancreatitis.
  - Isolated Grade 4 electrolyte imbalances/abnormalities that are not associated with clinical sequelae and are corrected with supplementation/appropriate management within 72 hours of their onset
  - Grade 4 drug-related endocrinopathies adequately controlled with only physiologic hormone replacement do not require discontinuation
- Any event that leads to delay in dosing lasting > 6 weeks from the previous dose requires discontinuation, with the following exceptions:
  - Dosing delays to allow for prolonged steroid tapers to manage drug-related adverse events are allowed. Tumor assessments should continue as per protocol even if dosing is delayed.

- Dosing delays lasting > 6 weeks from the previous dose that occur for non-study-drug-related reasons may be allowed. Tumor assessments should continue as per protocol even if dosing is delayed.

Any adverse event, laboratory abnormality, or intercurrent illness which, in the judgment of the Investigator, presents a substantial clinical risk to the subject with continued nivolumab dosing.

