### Nivolumab and Ipilimumab Dosing

Patients will receive treatment with nivolumab as a 30 minute infusion 3 mg/kg every 2 weeks and ipilimumab as a 30 minute infusion 1 mg/kg every 6 weeks, starting on Day 1, until progression, unacceptable toxicity, withdrawal of consent, or the study ends, whichever occurs first.

When nivolumab and ipilimumab are to be administered on the same day, separate infusion bags and filters must be used for each infusion. Nivolumab is to be administered first. The second infusion will always be ipilimumab and will start no sooner than 30 minutes after completion of the nivolumab infusion.

Nivolumab and ipilimumab may be diluted in 0.9% Sodium Chloride Solution or 5% Dextrose solution.

Dosing calculations should be based on the body weight assessed during screening. If the subject's weight on the day of dosing differs by > 10% from the weight used to calculate the prior dose, the dose must be recalculated. All doses should be rounded per local standards for rounding.

There will be no dose modifications allowed.

Subjects may be dosed with nivolumab no less than 12 days from the previous dose.

There are no premedications recommended.

Subjects should be carefully monitored for infusion reactions during nivolumab and/or ipilimumab administration. If an acute infusion reaction is noted, subjects should be managed according to Section 11.4.

Doses of nivolumab and/or ipilimumab may be interrupted, delayed, or discontinued depending on how well the subject tolerates the treatment. See Sections 11.5-11.7 for more details regarding dose delays, retreatment, and discontinuations.

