### 11.4 Management of Nivolumab or Ipilimumab-Related Infusion Reactions

Since nivolumab and ipilimumab contain only human immunoglobulin protein sequences, it is unlikely to be immunogenic and induce infusion or hypersensitivity reactions. However, if such a reaction were to occur, it might manifest with fever, chills, rigors, headache, rash, pruritus, arthralgias, hypotension, hypertension, bronchospasm, or other allergic-like reactions.

Infusion reactions should be graded according to NCI CTCAE (Version 4.0) guidelines.

Treatment recommendations are provided below and may be modified as appropriate:

- For **Grade 1** symptoms: (mild reaction; infusion interruption not indicated; intervention not indicated):
  - Remain at bedside and monitor subject until recovery from symptoms. The following prophylactic premedications are recommended for future infusions: diphenhydramine 50 mg (or equivalent) and/or acetaminophen/paracetamol 325 to 1000 mg at least 30 minutes before additional nivolumab administrations.
- For **Grade 2** symptoms: (moderate reaction required therapy or infusion interruption but responds promptly to symptomatic treatment (e.g., antihistamines, non-steroidal anti-inflammatory drugs, narcotics, corticosteroids, bronchodilators, IV fluids); prophylactic medications indicated for ≤ 24 hours):
  - Stop infusion, begin an IV infusion of normal saline, and treat the subject with diphenhydramine 50 mg IV (or equivalent) and/or acetaminophen/paracetamol 325 to 1000 mg; remain at bedside and monitor subject until resolution of symptoms. Corticosteroid and/or bronchodilator therapy may also be administered as

appropriate. If the infusion is interrupted, then restart the infusion at 50% of the original infusion rate when symptoms resolve; if no further complications ensue after 30 minutes, the rate may be increased to 100% of the original infusion rate. Monitor subject closely. If symptoms recur, then no further nivolumab will be administered at that visit. Administer diphenhydramine 50 mg IV, and remain at bedside and monitor the subject until resolution of symptoms. The amount of study drug infused must be recorded on the electronic case report form (eCRF).

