- For future infusions of therapy associated with infusion reaction, the following prophylactic premedications are recommended: diphenhydramine 50 mg (or equivalent) and/or acetaminophen/paracetamol 325 to 1000 mg should be administered at least 30 minutes before nivolumab infusions. If necessary, corticosteroids (up to 25 mg of Solu-Cortef or equivalent) may be used.
- For **Grade 3 or 4** symptoms: (severe reaction, Grade 3: prolonged [i.e., not rapidly responsive to symptomatic medication and/or brief interruption of infusion]; recurrence of symptoms following initial improvement; hospitalization indicated for other clinical sequelae (e.g., renal impairment, pulmonary infiltrates). Grade 4: Life-threatening; pressor or ventilatory support indicated):
  - Immediately discontinue infusion of study drug. Begin an IV infusion of normal saline and treat the subject as follows: Recommend bronchodilators, epinephrine 0.2 to 1 mg of a 1:1000 solution for subcutaneous administration or 0.1 to 0.25 mg of a 1:10,000 solution injected slowly for IV administration, and/or diphenhydramine 50 mg IV with methylprednisolone 100 mg IV (or equivalent), as needed. Subject should be monitored until the Investigator is comfortable that the symptoms will not recur. The study drug that is associated with infusion reaction will be permanently discontinued. Investigators should follow their institutional guidelines for the treatment of anaphylaxis. Remain at bedside and monitor subject until recovery of the symptoms.
  - In case of late-occurring hypersensitivity symptoms (e.g., appearance of a localized or generalized pruritus within 1 week after treatment), symptomatic treatment may be given (e.g., oral antihistamine or corticosteroids).

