### 13.0 CRITERIA FOR REMOVAL FROM STUDY

Nivolumab and ipilimumab treatment should be permanently discontinued for the following reasons and the specific reasons for removal from study will be documented:

- Patient withdrawal of consent at any time
  - Every effort should be made to obtain information on patients who withdraw from the study. The primary reason for withdrawal from the study should be documented. However, patients will not be followed for any reason after consent has been withdrawn.
- Termination of the study by MSKCC or BMS for any reason
- Radiographic progression: Confirmed disease progression per RECIST v1.1.
  - Patients who experience initial progressive disease may continue therapy if they are experiencing clinical benefit. A CT scan should be repeated no more than 6 weeks after the first documentation of progressive disease. If there is at least 10% more progression (e.g. first scan showed 24% growth relative to baseline, second scan shows 36% growth relative to baseline), then study therapy should be discontinued. If, instead, <10% further progression is seen, the patient may continue study therapy until confirmed progression of disease so long as there is continued clinical benefit.
- Clinical progression: Symptomatic deterioration attributed to disease progression as determined by the investigator after integrated assessment of radiographic data, biopsy results, and clinical status.
- Other conditions: Any medical condition that may jeopardize the patient's safety if he or she continues on study treatment.
- Pregnancy
- New therapies: Use of another systemic anti-cancer therapy.
  - Cases in which patients experience a mixed response requiring local therapy (e.g. surgery, stereotactic radiosurgery, radiotherapy, radiofrequency ablation) for control of tumor growth or symptoms may still be eligible to continue study treatment so long

as such therapy is not directed at a target lesion used for assessment of radiographic progression per RECIST v1.1 Such cases must be discussed with and approved by the Sponsor-PI.

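### For Grade 2 bronchospasm or another Grade 2 hypersensitivity reaction during an ipilimumab infusion, the advisory default in Section 11.4 is to restart the infusion, while Section 13.0 takes the patient off ipilimumab for good

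*Combined protocol and SAP*

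**What the plan says.** Two dosing texts, in Section 5.1 (Nivolumab and Ipilimumab Dosing) and Section 9.1 (Nivolumab and Ipilimumab), direct staff in the same way: "If an acute infusion reaction is noted, subjects should be managed according to Section 11.4". Both then point to Sections 11.5 to 11.7 for delays, retreatment and discontinuations.

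Section 11.4 covers reactions to either drug by its title. Its list of possible signs ends with "hypotension, hypertension, bronchospasm, or other allergic-like reactions". It opens its advice with "Treatment recommendations are provided below and may be modified as appropriate". For Grade 2 it says to stop the infusion and treat, and adds that "Corticosteroid and/or bronchodilator therapy may also be administered". The next sentence reads "If the infusion is interrupted, then restart the infusion at 50% of the original infusion rate when symptoms resolve". For later visits it says "For future infusions of therapy associated with infusion reaction, the following prophylactic premedications are recommended". It states permanent discontinuation of the causative drug only for Grade 3 or 4.

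Section 13.0 opens with "Nivolumab and ipilimumab treatment should be permanently discontinued for the following reasons". Its ipilimumab list contains "Any Grade 2-3 bronchospasm or other hypersensitivity reaction" and makes no exception for a reaction that arises during an infusion. The nivolumab list in the same section names bronchospasm, hypersensitivity reaction and infusion reaction as three separate terms and stops the drug for them from Grade 3.

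**The concern.** A nurse or physician dealing with bronchospasm during an ipilimumab infusion will open the section that the dosing text names. For Grade 2, that section leads to a restart at the same visit and envisages later premedicated doses. The removal section, which staff are not told to consult at that moment, says the patient should not receive ipilimumab again. Nothing in the protocol says which text prevails.

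What is at stake is patient safety: re-exposure to a drug that the protocol's own criteria withdraw. It is not a question of inference. Response is assessed by RECIST 1.1, and patients who stop treatment for toxicity stay on the scheduled tumour assessments, so neither reading changes an endpoint or an analysis.

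**Working it through.** No arithmetic applies, since the plan attaches no rate, threshold count or sample size to this event. The check is to set the two sections side by side and find where they disagree.

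**Step 1: which drug.** Section 11.4 covers both drugs. Parts of its Grade 2 text name only nivolumab (the recurrence sentence and the timing of premedication), but the title and the phrase introducing premedication refer to whichever therapy caused the reaction. Ipilimumab is therefore within its scope.

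**Step 2: what is being graded.** Section 11.4 grades the infusion reaction as a whole. The Section 13.0 ipilimumab item grades the bronchospasm or hypersensitivity reaction itself. These need not be the same grade, because a Grade 2 infusion reaction could include milder bronchospasm. The protocol does not reproduce the CTCAE scales, so it cannot show how often the two grades coincide.

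**Step 3: case by case.**

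| Event during infusion | Section 11.4 default | Section 13.0 | Conflict? |
|---|---|---|---|
| Ipilimumab, bronchospasm itself Grade 2 | Restart at half rate once resolved; premedicate later doses | Permanent stop | Yes |
| Ipilimumab, other reaction classed as hypersensitivity, itself Grade 2 | Same | Permanent stop | Yes |
| Ipilimumab, Grade 2 infusion reaction with no Grade 2 bronchospasm or hypersensitivity component | Same | Not on the list | No |
| Ipilimumab, Grade 3 bronchospasm or hypersensitivity reaction | Permanent stop | Permanent stop | No |
| Nivolumab, Grade 2 | Restart as above | These events are listed from Grade 3 | No |

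The first row needs no argument about classification, because bronchospasm is named in both sections. The second depends on the event being recorded as a hypersensitivity reaction, since the ipilimumab list does not mention infusion reactions as such.

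**Step 4: whether the linked sections close the gap.** Section 11.5 delays both drugs for drug-related non-skin events of Grade 2 or worse, but only until the Section 11.7 criteria are met. Section 11.7 contains no bar for bronchospasm or hypersensitivity. It does send a different Grade 2 event, combined transaminase and bilirubin elevation, to Section 13.0 by number. The authors therefore used such a reference elsewhere, but this event has none. Section 13.0 also requires ipilimumab discontinuation to be judged separately from nivolumab, but that instruction sits inside Section 13.0 itself.

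**Step 5: what the default would add.** The restart delivers the rest of a 1 mg/kg dose. How much remains depends on when in the 30-minute infusion the reaction began, so it could be anything from very little to nearly all of it. If symptoms recur after improving, Section 11.4 counts the reaction as Grade 3 and stops the drug. That protection acts only after re-exposure.

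**The case against.** The strongest reply is that the two sections can be read together. Section 11.4 offers recommendations that may be adapted, whereas Section 13.0 is a specific removal rule for ipilimumab. Adjustable advice can give way to a specific criterion without a precedence clause. An investigator who knows Section 13.0 can comply with both, and the general removal criteria and the last ipilimumab item also require stopping when continued dosing carries substantial risk. The nivolumab-only wording in parts of the Grade 2 text may mean that it was never fully adapted for ipilimumab. The event is also described as unlikely.

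Much of this stands. It shows that the protocol does not compel a restart. It does not cure the default: permission to modify advice does not tell bedside staff that this event must be handled differently, and none of the sections they are sent to says so.

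A reader might infer more than the documents support:

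- *That every Grade 2 ipilimumab infusion reaction is in conflict.* It is not. The ipilimumab list omits infusion reactions as a term, and its grade belongs to the bronchospasm or hypersensitivity event.
- *That the next six-weekly dose would follow automatically.* It would not. The delay rule in Section 11.5 and the separate ipilimumab assessment in Section 13.0 both stand in the way, although neither section that staff are sent to expressly forbids the dose.
- *That nivolumab is affected.* It is not, because its threshold agrees with Section 11.4.

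**Conclusion.** The concern holds within narrow limits. When bronchospasm or another hypersensitivity reaction that is itself Grade 2 occurs during an ipilimumab infusion, the advisory Section 11.4 default contradicts the Section 13.0 removal criterion, and no text that staff are directed to resolves the contradiction.

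The main exposure, per event, is one same-visit restart after symptoms have resolved. The documents give no event rate, so the number of the 30 planned patients affected cannot be estimated; it may well be none. The conclusion assumes only that the Section 13.0 ipilimumab item means what it says and includes reactions arising during infusion, since it makes no exception for them. It should be fixed because the instruction concerns an acute safety event and the correction is simple. It does not call the trial's design or analysis into question.

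**What to change.** Add to the Grade 2 text of Section 11.4: *If the reaction is to ipilimumab and includes bronchospasm or another hypersensitivity reaction of Grade 2, do not restart ipilimumab; discontinue it permanently per Section 13.0.* Add a matching reference to Section 11.4 beside the ipilimumab item in Section 13.0.

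Optional tidy-up in the same amendment: replace nivolumab with the study drug concerned in the Grade 2 recurrence and premedication sentences, and with ipilimumab in the last item of the ipilimumab list.

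The cost is one sentence and a cross-reference in a wording amendment, plus notice to staff at a single site. No threshold changes, and no visits, tests or patients are added.

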### 4.3 Intervention

Patients who are eligible and provide study consent will undergo screening procedures and evaluation by thoracic surgery (or other appropriate surgical/interventional radiological specialty) to discuss and plan standard-of-care surgical resection or biopsy (the biopsy is research non-billable unless performed for a standard-of-care reason).

In those patients undergoing a resection, the CT scan of the chest (+/- abdomen/pelvis depending on sites of known disease) which will serve as the baseline for this protocol must be obtained after surgical procedure or biopsy has taken place. For those undergoing biopsy, the CT scan can be performed before or after the biopsy but must be completed during the screening period. Additional screening procedures (including blood tests and EKG) may take place before or after surgical procedure or biopsy so long as they occur during the screening window. All screening procedures (including biopsies if performed) and scans must be done within 28 days of beginning study therapy with the exception of those undergoing tumor resections which may be performed within 12 weeks (84 days) before beginning study therapy so long as there has been no intervening systemic anti-cancer therapy.

Following resection/biopsy and screening procedures, patients will begin treatment with nivolumab IV 3mg/kg and ipilimumab 1mg/kg. Treatment with nivolumab will continue every 2 weeks (+/- 3 days) thereafter and treatment with ipilimumab will continue every 6 weeks (+/- 3 days) thereafter. Each treatment cycle will be defined as below:

- C1D1: Nivolumab 3mg/kg + Ipilimumab 1mg/kg
- C2D1 (+/- 3 days): Nivolumab 3mg/kg
- C3D1 (+/- 3 days): Nivolumab 3mg/kg
- C4D1 (+/- 3 days): Nivolumab 3mg/kg + Ipilimumab 1mg/kg

Treatment will continue until protocol-defined toxicity, confirmed progression of disease\*, withdrawal of consent, or death.

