### 11.5 Dose Delay Criteria

Dose delay criteria apply for all drug-related events (regardless of whether or not the event is attributed to nivolumab, ipilimumab or both).

Nivolumab and ipilimumab administration should be delayed for the following:

- Any Grade  $\geq 2$  non-skin, drug-related adverse event, with the following exceptions:
  - Grade 2 drug-related fatigue or laboratory abnormalities do not require a treatment delay.
- Any Grade 3 skin, drug-related adverse event
- Any Grade 3 drug-related laboratory abnormality, with the following exceptions for lymphopenia, AST, ALT, or total bilirubin or asymptomatic amylase or lipase:
  - Grade 3 lymphopenia does not require dose delay

- If a subject has a baseline AST, ALT or total bilirubin that is within normal limits, delay dosing for drug-related Grade  $\geq 2$  toxicity
- If a subject has baseline AST, ALT, or total bilirubin within the Grade 1 toxicity range, delay dosing for drug-related Grade  $\geq 3$  toxicity
- Any Grade  $\geq 3$  drug-related amylase or lipase abnormality that is not associated with symptoms or clinical manifestations of pancreatitis does not require dose delay.
- Any adverse event, laboratory abnormality, or intercurrent illness which, in the judgment of the investigator, warrants delaying the dose of study medication.

Patients who require delay of nivolumab or ipilimumab should be re-evaluated weekly or more frequently if clinically indicated. Both drugs should be delayed until re-treatment criteria are met (per Section 11.7).

Nivolumab may be delayed until the next planned ipilimumab dose if the next ipilimumab dose is scheduled within the next 12 days. This will permit periodic ipilimumab dosing to be synchronized with nivolumab dosing.

Ipilimumab should be dosed at the specified interval regardless of any delays in intervening nivolumab doses. However, in order to maintain periodic synchronized dosing of ipilimumab and nivolumab, the dosing days of nivolumab and ipilimumab may be adjusted within the permitted +/- 5 day window, as long as consecutive nivolumab doses are given at least 12 days apart. Ipilimumab may be delayed beyond the 5 day window if needed to synchronize with the next nivolumab dose.

If an ipilimumab dose is delayed beyond 6 weeks from the prior ipilimumab dose, then subsequent ipilimumab doses should be rescheduled to maintain the 6 week interval between consecutive ipilimumab doses.

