Dose delay of nivolumab which results in treatment interruption of  $> 6$  weeks or ipilimumab for  $> 12$  weeks require treatment discontinuation, with exceptions as noted in Section 13.0

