#### 11.7 Criteria to resume treatment

Patients may resume treatment with nivolumab when the drug-related AE(s) resolve(s) to Grade 1  $\leq$  or baseline, with the following exceptions:

- Patients may resume treatment in the presence of Grade 2 fatigue
- Patients who have not experienced a Grade 3 drug-related skin AE may resume treatment in the presence of Grade 2 skin toxicity
- Patients with baseline Grade 1 AST/ALT or total bilirubin who require dose delays for reasons other than a 2-grade shift in AST/ALT or total bilirubin may resume treatment in the presence of Grade 2 AST/ALT OR total bilirubin
- Patients with combined Grade 2 AST/ALT AND total bilirubin values meeting discontinuation parameters (Section 13.0) should have treatment permanently discontinued

- Drug-related pulmonary toxicity, diarrhea, or colitis must have resolved to baseline before treatment is resumed
- Drug-related endocrinopathies adequately controlled with only physiologic hormone replacement may resume treatment
- Subjects who received systemic corticosteroids for management of any drug-related toxicity must be off corticosteroids or have tapered down to an equivalent dose of prednisone □ 10 mg/day.
- Ipilimumab may not be resumed sooner than 6 weeks (+/- 5days) after the prior ipilimumab dose.
- In general, subjects who meet criteria to resume ipilimumab will also have met criteria to resume nivolumab, so it should be feasible to synchronize dosing of both drugs when resuming ipilimumab. In order to facilitate this, the dosing days of nivolumab and ipilimumab may be adjusted within the permitted +/- 5 day window, as long as consecutive nivolumab doses are given at least 12 days apart.
- In instances in which toxicity is felt to be exclusively related to ipilimumab, treatment with nivolumab alone may be resumed after retreatment criteria are met and after discussion with PI-Sponsor.

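### Section 13.0 ends ipilimumab for good when a non-exempt event delays it past 6 weeks, its planned interval, while Section 11.5 sets the limit at 12 weeks

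*Combined protocol and SAP*

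**What the plan says.** Section 4.3 (Intervention) sets the schedule: "treatment with ipilimumab will continue every 6 weeks (+/- 3 days) thereafter". Sections 11.5 and 11.7 work with a wider window of 5 days either side.

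Three places then govern a late ipilimumab dose.

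- **Section 13.0, ipilimumab discontinuation list:** "Any event that leads to delay in dosing lasting > 6 weeks from the previous dose requires discontinuation". Two exceptions follow: "Dosing delays to allow for prolonged steroid tapers to manage drug-related adverse events are allowed" and "Dosing delays lasting > 6 weeks from the previous dose that occur for non-study-drug-related reasons may be allowed". The nivolumab list in the same section has the same bullet, with the same 6-week figure and the same two exceptions.
- **Section 11.5, closing sentence:** discontinuation is triggered by a nivolumab interruption of more than 6 weeks or an ipilimumab interruption of more than 12; these "weeks require treatment discontinuation, with exceptions as noted in Section 13.0". No start point is given for either count.
- **Section 11.5, rescheduling:** "If an ipilimumab dose is delayed beyond 6 weeks from the prior ipilimumab dose, then subsequent ipilimumab doses should be rescheduled", so that the 6-week spacing is kept.

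Section 11.7 adds a lower bound: "Ipilimumab may not be resumed sooner than 6 weeks (+/- 5days) after the prior ipilimumab dose".

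**The concern.** A limit of 6 weeks from the previous dose suits a drug given every 2 weeks. For a drug given every 6 weeks it allows no delay past the due date. A patient whose ipilimumab is held on its due date for a drug-related event, and who recovers within a week or two without a prolonged steroid taper, would lose the drug permanently under Section 13.0. Under the closing sentence of Section 11.5 the same patient is well within the limit.

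Ipilimumab is half of the regimen whose response the trial studies, and this is a mandatory stopping rule. If one investigator works from Section 11.5 and another from Section 13.0, patients with the same short event will be treated differently, and those who resume will have breached Section 13.0.

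**Working it through.** The plan gives no calculated figure to reproduce. The check is day arithmetic plus a side-by-side reading.

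**Inputs.** Ipilimumab interval 6 weeks, window 3 days (Section 4.3) or 5 days (Sections 11.5 and 11.7). Ipilimumab limits: more than 6 weeks (Section 13.0) and more than 12 weeks (Section 11.5). Nivolumab: interval 2 weeks, limit more than 6 weeks in both sections.

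**Ipilimumab, in days after the previous dose.**

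- Due: 6 × 7 = 42.
- Windows end: 42 + 3 = 45, and 42 + 5 = 47.
- Section 13.0 limit: 6 × 7 = 42, so the rule applies from day 43. Slack past the due date: 42 − 42 = 0 days.
- Section 11.5 limit, counted from the previous dose: 12 × 7 = 84. Slack: 84 − 42 = 42 days.
- Days outside every permitted window on which Section 13.0 requires a stop and Section 11.5 does not: 48 to 84.

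**Nivolumab for comparison.** Due on day 14, limit on day 42 in both sections, slack 42 − 14 = 28 days. The two sections agree for nivolumab and disagree only for ipilimumab. The ipilimumab bullet looks carried over from the nivolumab list without changing the figure. That is an inference; the last item of the ipilimumab list, which still names nivolumab dosing, is consistent with it.

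**Does a different start point reconcile the limits?**

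| Count from | Nivolumab: 13.0 / 11.5 | Ipilimumab: 13.0 / 11.5 |
|---|---|---|
| Previous dose in both sections | 6 / 6 weeks | 6 / 12 weeks |
| Due date in both sections | 2 + 6 = 8 / 8 weeks | 6 + 6 = 12 / 6 + 12 = 18 weeks |
| Due date in 13.0, previous dose in 11.5 | 8 / 6 weeks | 12 / 12 weeks |

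Only the last row makes ipilimumab agree. It breaks the nivolumab agreement and sets aside the start point that Section 13.0 states.

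**Does the cross-reference reconcile them?** Section 11.5 defers to the exceptions in Section 13.0. Both exceptions permit longer delays; neither shortens 12 weeks to 6. If Section 13.0 governs, a non-exempt delay ends ipilimumab at 6 weeks, and an exempt delay is exempt from the 12-week limit too. The 12-week limit then never binds on anyone.

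**Example, with C1D1 as day 0.** Grade 2 drug-related diarrhea is present at C4D1 (day 42). Section 11.5 requires both drugs to be held and re-evaluation at least weekly. By day 49 the diarrhea is back to baseline without a prolonged steroid taper, which meets the resumption rule in Section 11.7.

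- Ipilimumab gap: 49 ÷ 7 = 7 weeks. Section 13.0 says stop; the 12-week limit is not reached.
- Nivolumab gap: last dose at C3D1 (day 28), so (49 − 28) ÷ 7 = 3 weeks. No conflict.
- If ipilimumab resumes on day 49, the Section 11.5 rescheduling rule puts the next dose on day 49 + 42 = 91, instead of day 84.

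**The case against.** The strongest reply is that both limits can be obeyed. Section 11.5 says when ipilimumab must stop and never requires it to resume, so stopping at 6 weeks breaches neither section. The stricter rule is also the safer one, and Section 13.0 is stricter for ipilimumab elsewhere: AST or ALT above 8 × ULN against 10 × ULN for nivolumab, and no 7-day allowance for grade 3 non-skin events. This stands to the extent that the documents do not establish which limit was meant. It does not explain why a 12-week limit was written that could never apply.

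A reader might also infer more than the text supports:

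- *That a one-day slip ends ipilimumab.* Literally, days 43 to 47 exceed 6 weeks. But a dose given inside a permitted window is ordinarily on schedule, not delayed. The firm range starts at day 48.
- *That the rescheduling sentence contradicts Section 13.0.* It is conditional and says when later doses fall, not who may continue. It can operate on exempt delays alone. It fits a 12-week limit better, but creates no conflict by itself.
- *That the synchronization sentence, "Ipilimumab may be delayed beyond the 5 day window if needed to synchronize with the next nivolumab dose", is a further contradiction.* A delay made only to line up the two drugs plausibly falls under the non-drug-related exception.
- *That the conflict runs to day 126.* This needs the 12 weeks to start at the missed dose (42 + 84 = 126). Section 11.5 matches the nivolumab rule in Section 13.0 only when counted from the previous dose, so day 84 is the supportable end.

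The affected group is also narrow. Most grade 3 non-skin drug-related events already end ipilimumab under Section 13.0, and prolonged tapers are exempt. What remains is mainly lower-grade events that coincide with an ipilimumab due date.

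**Conclusion.** The point holds as a conflict between two stated stopping limits for ipilimumab. For a drug-related event without a prolonged steroid taper, Section 13.0 stops the drug past 6 weeks from the previous dose and Section 11.5 past 12. The clear range of disagreement is days 48 to 84. This assumes that the Section 11.5 count runs from the previous dose, as the nivolumab figures indicate, and that a dose inside the 5-day window is not a delay.

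The consequence is confined to treatment conduct: ipilimumab is lost after brief, resolved events that Section 11.5 would let resume. No sample size, analysis or evaluability rule changes in this 30-patient descriptive study. Nivolumab may continue alone, although Section 13.0 stops both drugs if the investigator cannot tell which one the event relates to. How many patients would be affected cannot be worked out from the documents. It should be fixed because the rule is mandatory and the correction is small.

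**What to change.** In the ipilimumab list of Section 13.0, replace 6 weeks with 12 weeks in the delay bullet and in its non-drug-related exception, keeping the previous dose as the start point. In Section 11.5, state that the 12 weeks run from the previous ipilimumab dose. With this change the slack becomes 84 − 42 = 42 days in both sections.

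Because this loosens a mandatory stop, the sponsor-investigator must first confirm that 12 weeks is intended. If a stricter limit is wanted, set it beyond the dosing window (later than day 47) and change the 12-week figure in Section 11.5 to match.

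The cost is two figures and one clarifying phrase, with no added procedures, patients or analyses. As a separate editorial correction, the last item of the ipilimumab list should refer to ipilimumab dosing.
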